STATISTICAL ANALYSIS PLAN (SAP)

Physical activity after periacetabular osteotomy followed by progressive resistance training or progressive resistance training alone for hip dysplasia: secondary analysis of the randomized controlled PreserveHip trial

Trial ID: PreserveHip

Trial registration: ClinicalTrials.gov, NCT03941171

SAP version: Version 1.

Date: May 26, 2026.

Authors/Collaborators

[name], PT, PhD; [name], PhD; [name], PT, PhD; [name], PT, MSc; [name], PT, PhD Student; [name], PhD; [name], PhD; [name], PT, PhD, DMSc

Authors writing the SAP

[name], [name] and [name]

Senior biostatistician responsible

[name], BSc, MSc, PhD; Associate Professor at the Department of Biostatistics, Aarhus University

Chief investigator/clinical lead

[name], PT, PhD, DrMed

INTRODUCTION

Background

Hip dysplasia is characterised by insufficient acetabular coverage of the femoral head, leading to altered hip biomechanics and increased joint contact pressure (1-4). The condition is associated with hip pain, impaired function, and reduced physical activity, as well as an increased risk of hip osteoarthritis (5-9). Periacetabular osteotomy (PAO) is the standard surgical treatment, while non-surgical management, including progressive resistance training (PRT), has also been proposed as an alternative treatment option (10, 11).

Rationale for this study

The PreserveHip randomised controlled trial found no superiority of PAO followed by PRT compared with PRT alone for improvement in patient-reported hip pain among individuals with hip dysplasia eligible for PAO surgery (12). Previous studies have reported discordance between patient-reported outcomes and objectively measured functional outcomes (9, 13, 14). This secondary analysis was therefore conducted to investigate whether PAO followed by PRT, compared with PRT alone, is associated with differences in objectively measured physical activity one year after initiation of treatment.

Aims

Primary efficacy aim: To compare the objectively measured daily number of steps one year after initiation of treatment between participants randomised to PAO followed by PRT and participants randomised to PRT alone.

Secondary aim: To compare the objectively measured daily number of steps one year after initiation of treatment in participants with hip dysplasia to daily step counts in healthy subjects.

Tertiary aim: To investigate the association between objectively measured daily number of steps and patient-reported hip outcomes one year after initiation of treatment.

STUDY METHODS

Trial design

This study is a secondary analysis of data from the PreserveHip trial, a multicentre randomised controlled trial conducted at Aarhus University Hospital and Odense University Hospital in Denmark and at Oslo University Hospital in Norway. The PreserveHip trial was designed as a parallel-group superiority trial with a 1:1 allocation ratio. Participants were randomly assigned to either PAO followed by usual care and eight months of PRT or 12 months of PRT alone. The present secondary analysis focuses on objectively measured physical activity outcomes assessed one year after initiation of treatment. Analyses comparing the two intervention groups preserve the original randomisation. Comparisons with healthy subjects are observational and non-randomised. We prespecified and registered the PreserveHip

trial at ClinicalTrials.gov (NCT03941171), and we have previously published the trial protocol (15) and the blinded interpretation of the primary results (16). This statistical analysis plan (SAP) is reported in line with the ‘Guidelines for the Content of Statistical Analysis Plans in Clinical Trials’ (17), while the reporting of this secondary analysis will follow the “Consolidated Standards of Reporting Trials” (CONSORT) statement (18).

Randomization and blinding

After completion of baseline assessments, participants were randomised in a 1:1 ratio to either PAO followed by PRT or PRT alone. Randomisation was performed using a computer-generated allocation sequence implemented in REDCap (19, 20), with permuted blocks of variable size (4, 6, and 8). Allocation concealment was ensured through an external randomisation service provided by the Clinical Trial Unit, Department of Clinical Medicine, Aarhus University, Denmark. Due to the nature of the interventions, participants were not blinded to treatment allocation, whereas outcome assessors performing follow-up assessments were blinded.

Sample size and power considerations

The PreserveHip trial was originally designed and powered for the primary outcome of patient-reported hip pain measured using the Hip disability and Osteoarthritis Outcome Score (HAGOS) (21). Prior to trial initiation, sample size calculations estimated that 48 participants per group would provide 80% power to detect a between-group difference in change from baseline to 12 months of 9.7 points on the HAGOS pain subscale, assuming a standard deviation of 16.2 and allowing for dropouts and crossovers (15). No formal sample size or power calculation was performed for the present secondary analysis of objectively measured physical activity. All analyses will be based on the analysis population defined below. Results from the present analyses will therefore be interpreted with consideration of their exploratory nature.

Statistical interim analyses and stopping guidance

No interim analyses were performed during the PreserveHip trial. Trial enrolment was discontinued before reaching the originally planned sample size due to slow participant recruitment. Trial enrolment and attrition rates were monitored throughout the study.

Timing of final analysis and outcome assessments

Outcome assessments for this secondary analysis of the PreserveHip trial were conducted at two time points: baseline and one year after initiation of the assigned treatment. The timing of the one-year follow-up assessment was defined as 12 months after treatment initiation, irrespective of randomization group. The specific time points for all outcome measurements were prespecified and are described in the published trial protocol (15).

STATISTICAL PRINCIPLES

Confidence intervals and p-values

All statistical tests will be two-sided and 95% confidence intervals (95% CIs) will be reported for all estimated effects. Statistical significance will be evaluated at a nominal significance level of 0.05 ($P < 0.05$) for all outcomes. No formal adjustment for multiple comparisons will be applied.

Analysis populations

The primary analysis will be conducted in a modified intention-to-treat (mITT) population, defined as all randomised participants with valid baseline physical activity measurements. Valid physical activity measurements are defined as at least three valid days with a minimum of 10 hours of accelerometer wear time per day. This criterion is required for inclusion in the statistical analyses and for imputation of the one-year outcome. Randomised participants who do not meet this criterion will be excluded from the analyses. Activity measure from participants included in the mITT population will be analysed according to their originally assigned randomization group, irrespective of treatment adherence or treatment crossover. This population represents the treatment policy estimand and will be used for all analyses comparing participants randomised to PAO followed by PRT with participants randomised to PRT alone.

A sensitivity analysis following the same approach as the primary analysis will be performed based on the complete-case population. The complete-case population is defined as all randomised participants with both valid baseline and follow-up physical activity measurements.

Healthy subjects with valid physical activity measurements meeting the same accelerometer wear-time criteria will be included in a separate observational analysis population. Comparisons involving healthy subjects are non-randomised and exploratory.

TRIAL POPULATION

Eligibility

Screening and recruitment were conducted in accordance with the prespecified eligibility criteria of the PreserveHip trial protocol (15). Participants with hip dysplasia were recruited following referral from primary care to the Departments of Orthopaedics at Aarhus University Hospital and Odense University Hospital in Denmark and Oslo University Hospital in Norway. Eligibility was assessed based on demographic, clinical, and radiographic information, and detailed inclusion and exclusion criteria are described in the published trial protocol (15). Eligible participants were invited to enrol after confirmation of eligibility and provision of written informed consent. Healthy subjects were recruited through networks associated with the PreserveHip trial and through advertisements at Aarhus University, VIA University College, and Aarhus University Hospital. Healthy subjects were aged 18–40 years, had no hip-related symptoms, and fulfilled prespecified criteria for hip function and general health. Screening and recruitment

data, including numbers screened, eligible and enrolled, will be summarised descriptively and reported in a CONSORT flow diagram.

Baseline patient characteristics

Baseline characteristics of randomised participants in the PAO and PRT groups and of healthy subjects will be presented descriptively (Table 1). Continuous variables will be summarised as means with standard deviations or medians with interquartile ranges, and categorical variables as counts and percentages. No statistical testing will be performed to compare baseline characteristics between groups, as baseline tables are intended solely to describe the study population before treatment initiation.

STATISTICAL ANALYSIS

Outcome definitions and endpoints

The primary outcome is the objectively measured daily number of steps at one year after initiation of treatment, assessed using tri-axial accelerometry (AX3, Axivity Ltd., Newcastle, UK) with data post-processed using a custom-designed algorithm implemented in MATLAB (22, 23). The primary endpoint is the between-group difference in the estimated mean daily number of steps at one year between participants randomised to PAO followed by PRT and participants randomised to PRT alone. Baseline number of steps and the site of inclusion will be included as covariates in the statistical model. All physical activity-related outcomes are presented in Table 2. Additionally, the six dimensions of HAGOS will be used to assess patient-reported outcomes (21).

Analysis methods

Primary and secondary physical activity outcomes will be analysed using analysis of covariance (ANCOVA) models. For comparisons between randomised treatment groups, the outcome measured at one year will be modelled with randomization group as the main factor. The corresponding baseline value of the outcome and site of inclusion will be included as covariates to reduce random variation. The primary estimand is the between-group difference at one year, and results will be reported as adjusted mean differences with corresponding two-sided 95% confidence intervals. A sensitivity analysis following the same approach as the primary analysis will be performed based on the complete-case population.

Comparisons involving healthy subjects will be analysed using multiple linear regression with the outcome being activity measured at one year for the two intervention groups and activity measured at baseline for the healthy subjects. The groups will be the main factor and the analysis will be adjusted for age and sex. These comparisons are observational and exploratory.

Associations between objectively measured physical activity outcomes and HAGOS scores will also be analysed using multiple linear regression models, adjusted for age and sex. To assess whether the association between physical activity and HAGOS differs between randomisation groups, an interaction term between physical activity and randomisation group will be included in the model.

Missing data

Inclusion in the analysis requires valid baseline physical activity measurements and participants without baseline physical activity measurements will be excluded from the analysis. Missing outcome data at one year for randomised participants will be handled using multiple imputation for all three aims, under the assumption that data are missing at random. Imputation will be performed using a regression model including baseline physical activity, age, sex, randomization group and site of inclusion as predictors. A total of 1,000 imputed datasets will be generated, and estimates will be combined using Rubin's rules (24). Healthy subjects will be analysed using observed data only. A sensitivity analysis of complete cases (participants with complete follow-up) will be performed for all three aims.

Statistical software

All statistical analyses will be performed using Stata version 19.5 (StataCorp LLC, College Station, TX, USA).

Tables

Table 1. Baseline characteristics of the modified intention-to-treat population and healthy subjects.

	PAO-group n = xx	PRT-group n = xx	Healthy-group n = xx
Female, n (%)			
Age (years), mean (SD) or median (IQR)			
BMI (kg/m ²), mean (SD) or median (IQR)			
Duration of hip symptoms, n (%)			
None			
0-6 months			
6-12 months			
1-2 years			
2-5 years			
5-10 years			
More than 10 years			
Missing			
Civil status, n (%)			
Married			
Cohabiting			
Single			
Divorced			
Widow/widower			
Not informed			
Educational level, n (%)			
Primary school			
Vocational education			
High school or similar			
Short higher education			
Medium higher education			
Long higher education			
Other education			
Employment status, n (%)			
During education			
In work			
In employment activation, sick leave, available, etc.			
Outside the labour market			
Alcohol consumption, n (%)			
Below 2 items per week			
2-7 items per week			
8-14 items per week			
Above 15 items per week			
Missing			
Smoking behaviour, n (%)			
Never smoked			
Quit smoking			
Sometimes			
Daily			

Outcomes will be presented as means with standard deviation (SD) or medians with interquartile range (IQR) or numbers (n) with proportion (%). PAO = Periacetabular osteotomy. CE-angle = Wibergs centre edge angle. AI-angle = Acetabular Index angle.

Table 2. Physical activity-related outcomes.

Dimension	Outcome	Timeframe	Unit
Frequency	Steps	One-year after initiating treatment	Number per day
	Cycling rotations	One-year after initiating treatment	Number per day
Intensity	Average cadence	One-year after initiating treatment	Steps per minute
	Very-low intensity activity	One-year after initiating treatment	Percentage per day
	Low intensity activity	One-year after initiating treatment	Percentage per day
	Moderate intensity activity	One-year after initiating treatment	Percentage per day
	High intensity activity	One-year after initiating treatment	Percentage per day
Time	Wear time	One-year after initiating treatment	Hours per day
	Walking	One-year after initiating treatment	Hours per day
	Standing	One-year after initiating treatment	Hours per day
	Sedentary	One-year after initiating treatment	Hours per day
	Cycling	One-year after initiating treatment	Minutes per day
Type	Sit to stand transfers	One-year after initiating treatment	Number per day
	Short walking bouts	One-year after initiating treatment	Number per day

Table 3. Physical activity per day described by the dimensions of F.I.T.T. measured one year after periacetabular osteotomy (PAO) for the PAO-group and one year after initiation of progressive resistance training (PRT) for the PRT-group.

Outcomes, mean (95% CI)		PAO-group			PRT-group			Adjusted between-group difference ^a	
		Baseline	One-year	Change	Baseline	One-year	Change	One-year	P-value
Frequency	Steps, n								
	Cycling rotations, n								
Intensity	Average cadence, steps/min								
	Very-low intensity activity, %								
	Low intensity activity, %								
	Moderate intensity activity, %								
	High intensity activity, %								
Time	Wear time, h								
	Walking, h								
	Standing, h								
	Sedentary, h								
	Cycling, min								
Type	Sit to stand transfers, n								
	Short walking bouts, n								

Analysis of covariance with multiple imputations for missing data, based on the modified intention-to-treat population. Results presented as mean with 95% confidence intervals (95% CI). ^aAdjusted for the number of steps at baseline and site of inclusion. Abbreviations: F.I.T.T. = frequency, intensity, time and type; H = hours. Min = minutes. N = number. PAO=Periacetabular osteotomy; PRT = Progressive resistance training

Table 4. Physical activity per day described by the dimensions of F.I.T.T. measured one year after periacetabular osteotomy (PAO) for the PAO-group, one year after initiation of progressive resistance training (PRT) for the PRT-group and at baseline for the healthy-group.

Outcomes, mean (95% CI)	Healthy-group Crude mean	Comparison with the PAO-group		Comparison with the PRT-group	
		Adjusted difference ^a	P-value	Adjusted difference ^a	P-value
Frequency					
Steps, number					
Cycling rotations, n					
Intensity					
Average cadence, steps/min					
Very low intensity activity, %					
Low intensity activity, %					
Moderate intensity activity, %					
High intensity activity, %					
Time					
Wear time, h					
Walking, h					
Standing, h					
Sedentary, h					
Cycling, min					
Type					
Sit to stand transfers, n					
Short walking bouts, n					

Results are presented as mean with 95% confidence intervals (95% CI). ^aAdjusted for age and sex. Abbreviations: F.I.T.T. = frequency, intensity, time and type; H = hours. Min = minutes. N = number. PAO=Periacetabular osteotomy; PRT = Progressive resistance training

Table 5. Association between number of daily steps and the Copenhagen Hip and Groin Outcome Score (HAGOS)

HAGOS	Crude analysis		Adjusted analysis		
	Steps, β (95% CI)	P	Steps, β (95% CI)	R ²	P
Symptoms					
Pain					
Physical function in daily living					
Physical function in sport and recreation					
Participation in physical activities					
Hip and/or groin-related quality of life					

Analysis adjusted for age and sex. CI: Confidence interval. HAGOS: the Copenhagen Hip and Groin Outcome Score. P: P-value. PAO: Periacetabular osteotomy. PRT: Progressive resistance training. R²: Coefficient of determination. β : Regression coefficient

REFERENCES

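### The adjusted steps-HAGOS models leave out site of inclusion, so a site difference in both measures, if there is one, can enter the slope (minor, exploratory aim)

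*SAP*

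**What the plan says.** The tertiary aim (SAP, Aims) is: "To investigate the association between objectively measured daily number of steps and patient-reported hip outcomes one year after initiation of treatment".

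The model is set out in the SAP under Analysis methods: "Associations between objectively measured physical activity outcomes and HAGOS scores will also be analysed using multiple linear regression models, adjusted for age and sex". The same paragraph adds that "an interaction term between physical activity and randomisation group will be included in the model". The Table 5 footnote repeats the covariates: "Analysis adjusted for age and sex". Table 5 has a crude column and an adjusted column for each of the six HAGOS dimensions.

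Site appears elsewhere in the same plan:
- Trial design: the trial was "conducted at Aarhus University Hospital and Odense University Hospital in Denmark and at Oslo University Hospital in Norway".
- Analysis methods, randomised comparison: "The corresponding baseline value of the outcome and site of inclusion will be included as covariates to reduce random variation".
- Missing data: imputation uses a "regression model including baseline physical activity, age, sex, randomization group and site of inclusion as predictors", for all three aims.

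The SAP gives no reason for leaving site out of the association models. It reports no site means, site shares or final number of patients.

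**The concern.** The randomised comparison is protected by design, and site enters it for precision. The steps-HAGOS slope has no such protection. Patients were randomised to a treatment, not to a step count, and both variables are measured one year after treatment starts. The slope is estimated between patients, who come from three hospitals in two countries.

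Suppose patients at one hospital walk more and also score higher on HAGOS for reasons unrelated to how much they walk. A model without site then attributes part of that hospital contrast to steps. The adjusted column of Table 5 would mix the association among patients at the same hospital with a difference between hospitals. The mixture could inflate the slope or mask it, depending on the direction of the two differences.

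**Working it through.** **No figure to reproduce.** The SAP gives no number for this association, so the check is an omitted-variable calculation on stated assumptions.

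**Inputs**
- From the SAP: three sites; planned size 2 × 48 = 96, with enrolment stopped before the plan was reached (final number not given); a design SD of 16.2 for HAGOS pain, borrowed here as the residual SD.
- Assumed: site shares 60/20/20%; within-site step SD 3,000; true slope 1.5 points per 1,000 steps; one of the smaller sites differs by *ds* = 500 to 1,500 steps and *dh* = 5 to 10 HAGOS points; 60 patients as a lower bound on N.

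**Formula.** With one site of share 0.2 shifted, the between-site factor is 0.2 × 0.8 = 0.16. What biases the slope is the site's direct effect on HAGOS at equal steps. The part of the HAGOS gap explained by the extra steps must therefore come off first:

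direct effect = *dh* − 1.5 × *ds*/1,000

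shift per step = 0.16 × *ds* × direct effect / (3,000² + 0.16 × *ds*²)

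**Results, both differences in the same direction**

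| ds (steps) | dh (points) | Direct effect | Calculation | Shift per 1,000 steps |
|---|---|---|---|---|
| 500 | 5 | 4.25 | 340 / 9,040,000 | 0.038 |
| 1,000 | 10 | 8.50 | 1,360 / 9,160,000 | 0.148 |
| 1,500 | 10 | 7.75 | 1,860 / 9,360,000 | 0.199 |

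Against the assumed slope of 1.5, this is 0.038/1.5 = 3% to 0.199/1.5 = 13%.

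**Compared with sampling error.** The standard error of the slope per 1,000 steps is about 16.2 / (3 × √N). This is 0.55 at N = 96 and 0.70 at N = 60. The largest shift above is 0.199/0.55 = 0.36 of a standard error at N = 96 and 0.199/0.70 = 0.28 at N = 60.

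**Opposite directions.** With *ds* = 1,500 and *dh* = −10, the direct effect is −12.25 and the shift is −2,940 / 9,360,000, or −0.31 per 1,000 steps. That is 0.57 of a standard error at N = 96.

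**Other site shares, in within-site SD units.** One site differs by the same number of SDs in steps and in the direct HAGOS effect, with shares from 80/10/10 to 50/50:
- 0.2 to 0.5 SD: the standardised slope shifts by 0.004 to 0.06.
- 0.8 SD: it shifts by 0.05 to 0.14.
- Site affects steps only: the shift is 0.

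**Cost of adding site.** For a standardised slope of 0.3, the standard error is √(0.91/(N − k)), with k = 6 parameters without site and 8 with it:
- N = 60: 0.130 becomes 0.132.
- N = 96: 0.101 becomes 0.102.

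Site adjustment also removes between-site variation in steps. In the largest case tabulated this multiplies the standard error by √(9.36/9.00) = 1.02.

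**The case against.** The best defence is that nothing here is wrong or contradictory. The text and the Table 5 footnote agree. The stated reason for site in the ANCOVA is to reduce random variation, and leaving it out of a different model with a different outcome does not conflict with that. The aim is to investigate an association, without a causal claim, and the SAP says its results will be read as exploratory. For a purely descriptive purpose the pooled slope is a legitimate quantity, and part of a between-site difference, such as case mix, may belong to it. All of this stands, and it is why the point is minor. It does not remove the case for site in the adjusted column, because the crude column already gives the pooled slope.

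Some stronger readings are tempting, but the SAP does not support them:
- *Site differences do distort the slope.* The SAP reports no site difference in steps or HAGOS, and does not describe different treating teams or different questionnaire settings.
- *The plan contradicts itself because site is in the imputation model.* One imputation model serves all three aims, and the ANCOVA contains site, so site belongs there regardless. An imputation model may be larger than an analysis model; baseline activity is also in it without being named for the association models.
- *Age and sex are the only other terms.* The interaction with randomisation group is there too, although it does not control for site.
- *The interaction is distorted because randomisation was not stratified by site.* The SAP names no site strata, but the protocol is not shown, so this would rest on silence.
- *The whole HAGOS gap between sites biases the slope.* Using *dh* without removing the part carried by steps gives 0.044 to 0.256 per 1,000 steps, which overstates the same-direction shift.

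**Conclusion.** The point holds as a minor improvement. The adjusted association models omit a variable that is already collected, is used in the randomised analysis, and can confound a comparison that randomisation does not protect.

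Under the assumptions listed, a same-direction site difference shifts the slope by about 0.04 to 0.20 points per 1,000 steps. That is 3 to 13% of the assumed slope and less than half a standard error for 60 to 96 patients. Opposite directions can take it slightly above half a standard error at N = 96. A shift as large as a standard error needs something like a 0.8 SD difference between sites in both measures. The shift is zero if site has no direct effect on HAGOS or if sites do not differ in steps. Every site input is an assumption, so these figures show scale and do not predict the bias in this trial.

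The randomised comparison is unaffected.

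**What to change.** Add site of inclusion as a categorical covariate to the adjusted steps-HAGOS models in Analysis methods. Change the Table 5 footnote to say that the analysis is adjusted for age, sex and site of inclusion. Keep the crude column as it is, so that the pooled association remains visible. If site is to stay out, give the reason in the SAP.

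The cost is a wording change, two degrees of freedom and a negligible change in the standard error. No new data are needed. Fixing it now also avoids a decision about site after the results are seen.

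### Table 5 has one adjusted steps coefficient per HAGOS subscale, but the Analysis methods text puts a steps-by-group interaction in the model, so the printed slope could belong to the reference arm only

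*SAP*

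**What the plan says.** The tertiary aim (SAP, Aims) is "To investigate the association between objectively measured daily number of steps and patient-reported hip outcomes one year after initiation of treatment". It asks for one association, not one per arm.

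Under Analysis methods, associations between physical activity and HAGOS "will also be analysed using multiple linear regression models, adjusted for age and sex". The next sentence begins "To assess whether the association between physical activity and HAGOS differs between randomisation groups" and continues that "an interaction term between physical activity and randomisation group will be included in the model". The SAP describes no separate model without the interaction and states neither the coding of the arms nor a reference arm.

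Table 5 has one row for each of the six HAGOS subscales. Each row has a crude steps coefficient with interval and P-value, and an adjusted steps coefficient with interval, R² and P-value. There is no cell for an interaction estimate, an interaction P-value or arm-specific slopes. The footnote reads "Analysis adjusted for age and sex". It also spells out the abbreviations PAO and PRT, although neither appears in the table.

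**The concern.** Once a product of steps and group is in a regression, the coefficient on steps alone no longer describes the whole sample. With indicator coding it describes the arm coded 0. The methods text speaks of one model and the table has one coefficient, so an analyst following both literally would print a reference-arm slope under a title that promises the overall association.

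Three things would follow:

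- The answer to the tertiary aim would depend on an arbitrary coding choice that the SAP does not fix.
- The interval would be wider than necessary, so a real association could look inconclusive.
- If the crude model has no interaction, the crude and adjusted columns would estimate different quantities, and a gap between them could be misread as confounding by age and sex.

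**Working it through.** The SAP states no figure for this point, so there is none to reproduce. The check is algebra, followed by a simulation under assumed values.

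**Inputs from the SAP.** Linear regression; age and sex as covariates; a physical activity by group interaction; 1:1 allocation (Trial design); one adjusted steps coefficient per subscale (Table 5).

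**Meaning of the coefficient.** Write the model as

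HAGOS = b0 + b1·steps + b2·group + b3·steps×group + age + sex, with group coded 0 or 1.

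- Slope in the arm coded 0: b1.
- Slope in the arm coded 1: b1 + b3.
- Average slope under 1:1 allocation: b1 + b3/2.

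The line a program labels as steps is b1. Reversing the coding replaces it with b1 + b3. This needs no assumption about the data.

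**Precision.** With m participants per arm, residual SD σ and step SD s, the standard error of a single-arm slope is about σ/(s√m), and that of the common slope about σ/(s√(2m)). The ratio is √2 ≈ 1.41, whatever the values of σ, s and m. With the assumed values below, 16/(2.5×√40) = 1.01 and 16/(2.5×√80) = 0.72.

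**Simulation.** Assumed values, none of them given in the SAP: 40 per arm, steps in thousands with mean 7 and SD 2.5, residual SD 16, an arm difference of 5 HAGOS points at zero steps, no missing data, 400 runs per row. Cells show the mean steps coefficient, with the mean standard error in brackets, in HAGOS points per 1,000 steps.

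| True slopes (PRT, PAO) | With interaction, PRT as reference | With interaction, PAO as reference | No interaction, group included | No interaction, age and sex only |
|---|---|---|---|---|
| 0, 2 | -0.09 (1.07) | 2.04 (1.05) | 0.98 (0.75) | 0.94 (0.87) |
| 0.5, 1.5 | 0.56 (1.05) | 1.53 (1.06) | 1.04 (0.74) | 1.02 (0.79) |
| 1, 1 | 0.96 (1.05) | 1.13 (1.06) | 1.04 (0.74) | 1.04 (0.74) |
| 2, 0 | 1.93 (1.05) | 0.02 (1.06) | 0.98 (0.75) | 0.97 (0.77) |

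The true average slope is 1 in every row. The simulation standard error of a reference-arm mean is about 1.05/√400 ≈ 0.05, so departures of around 0.1 are largely noise.

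- Unequal slopes: the interaction model's steps coefficient follows the reference arm and moves by about 1 to 2 points per 1,000 steps when the coding is reversed.
- Equal slopes: all versions centre on about 1, but the standard error is 1.05 against 0.74, a ratio of 1.42.
- Against the age-and-sex model without group, the ratio is smaller when the arms differ markedly in HAGOS, for example 1.07/0.87 = 1.23 in the first row, because the unmodelled arm difference adds residual spread.

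**The case against.** The strongest reply is that the two sentences in Analysis methods describe two steps. The first gives the association model with age and sex. The second opens with its own purpose and adds the interaction for that purpose only. The Table 5 footnote names age and sex alone, which fits the first model, and on that reading no reference-arm slope is printed. This reading is possible. It does, however, need a second model that the SAP never describes, and it leaves the question of effect modification without a cell in Table 5 or in the appendix. A clarification is needed on either reading.

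Coding of ±0.5 would make the steps coefficient the equal-weight average slope. That is true, but the SAP specifies no such coding.

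A reader might go further in two directions, and the document does not support either:

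- That group is left out as a main effect, so that an arm difference in HAGOS would appear as an interaction. The SAP does not say this. Age and sex are listed as the covariates of the association model, and including lower-order terms with an interaction is ordinary practice. The size of any such bias would rest on an assumed arm difference.
- That the interaction result will go unreported. The Confidence intervals and p-values section promises a 95% interval for every estimated effect, and the table shells are not exhaustive: complete-case analyses are planned for all three aims, but the appendix has a shell only for the primary one. A missing cell does not show a missing result.

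It is also fair to say that whether the overall association should be conditioned on group is a choice of estimand and not an error.

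**Conclusion.** The text and Table 5 do not fit together as written. Followed literally with 0/1 coding, they give a reference-arm slope where the tertiary aim asks for an overall association. That slope changes with arm coding if the arms differ, and its standard error is about 1.4 times that of the common slope even if they do not. The meaning of the coefficient and the √2 ratio follow from algebra (equal arms, similar spread of steps). The simulated slopes only illustrate this and depend on the assumed values.

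The conclusion is conditional on the adjusted columns being filled from the interaction model with indicator coding. A crude model without the interaction is unaffected, and so are the primary comparison of the arms and the comparison with healthy subjects. The SAP describes its results as exploratory and this is its tertiary aim, so the severity is minor to moderate.

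**What to change.** In Analysis methods, describe two models for each HAGOS subscale:

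1. HAGOS on steps, age and sex, without the interaction. State that the adjusted coefficient, interval, R² and P-value in Table 5 come from this model. Adding group is optional; if it is added, name it in the footnote.
2. HAGOS on steps, group, steps×group, age and sex, used only to assess effect modification. State the coding of the arms.

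Report from the second model the interaction estimate with its 95% interval and P-value, and both arm-specific slopes, in added columns of Table 5 or in an appendix table.

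The cost is a few sentences and a few columns. No new data are needed and no other analysis changes. The wording should be settled before the tertiary analysis is run, so that the choice of model is not made with the results in view.
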